8.2.2 Timing of Dose Administration

Trial treatment should be administered on Day 1 of each cycle after all procedures/assessments have been completed as detailed on the Trial Flow Chart (Section 6.0). Trial treatment may be administered up to 3 days before or after the scheduled Day 1 of each cycle due to administrative reasons.

All trial treatments will be administered on an outpatient basis.

Pembrolizumab 200 mg will be administered as a 30 minute IV infusion every 3 weeks. Sites should make every effort to target infusion timing to be as close to 30 minutes as possible. However, given the variability of infusion pumps from site to site, a window of -5 minutes and +10 minutes is permitted (i.e., infusion time is 30 minutes: -5 min/+10 min).

8.2.3 Trial Blinding/Masking

This is an open-label trial; therefore, the investigator and subject will know the treatment administered.

8.3 Concomitant Medications/Vaccinations (allowed & prohibited)

Medications or vaccinations specifically prohibited in the exclusion criteria are not allowed during the ongoing trial. If there is a clinical indication for one of these or other medications or vaccinations specifically prohibited during the trial, discontinuation from trial therapy or vaccination may be required. The investigator should discuss any questions regarding this with the Merck Clinical team. The final decision on any supportive therapy or vaccination rests with the investigator and/or the subject's primary physician.

8.3.1 Acceptable Concomitant Medications

All treatments that the investigator considers necessary for a subject's welfare may be administered at the discretion of the investigator in keeping with the community standards of medical care. All concomitant medication will be recorded on the case report form (CRF) including all prescription, over-the-counter (OTC), herbal supplements, and IV medications and fluids. If changes occur during the trial period, documentation of drug dosage, frequency, route, and date may also be included on the CRF.

All concomitant medications received within 28 days before the first dose of trial treatment and 30 days after the last dose of trial treatment should be recorded. Concomitant medications administered after 30 days after the last dose of trial treatment should be recorded for SAEs and ECIs as defined in Section 7.2.

8.3.2 Prohibited Concomitant Medications

Subjects are prohibited from receiving the following therapies during the Screening and Treatment Phase (including retreatment for post-complete response relapse) of this trial:

- Antineoplastic systemic chemotherapy or biological therapy
- Immunotherapy not specified in this protocol
- Chemotherapy not specified in this protocol
- Investigational agents other than pembrolizumab
- Radiation therapy
 - Note: Radiation therapy to a symptomatic solitary lesion or to the brain may be allowed at the investigator's discretion.
- Live vaccines within 30 days prior to the first dose of trial treatment and while participating in the trial. Examples of live vaccines include, but are not limited to, the following: measles, mumps, rubella, varicella/zoster, yellow fever, rabies, BCG, and typhoid vaccine.
- Systemic glucocorticoids for any purpose other than to modulate symptoms from an event of clinical interest of suspected immunologic etiology. The use of physiologic doses of corticosteroids may be approved after consultation with the Merk.

Subjects who, in the assessment by the investigator, require the use of any of the aforementioned treatments for clinical management should be removed from the trial. Subjects may receive other medications that the investigator deems to be medically necessary.

The Exclusion Criteria describes other medications which are prohibited in this trial.

There are no prohibited therapies during the Post-Treatment Follow-up Phase.

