5.0 TRIAL DESIGN

5.1 Trial Design

This is a single-arm, single-center, open-label trial of pembrolizumab (MK-3475) in subjects with advanced gastric or gastroesophageal junction (GEJ) adenocarcinoma who have progressed after failure of any combination chemotherapy containing a platinum and a fluoropyrimidine agent.

Approximately 40 subjects will be enrollment to evaluate the efficacy and safety of pembrolizumab.

Enrollment will begin with all subjects without regard for PD-L1 expression status.

An evaluable specimen for PD-L1 status must be available and confirmed prior to enrollment.

All study subjects will be evaluated every 6 weeks (+/- 7 days) following the date of IP drug administration for the first six months and every 12 weeks (+/- 7 days) thereafter until progression of disease is documented with radiologic imaging (computed tomography or magnetic resonance imaging).

The primary efficacy endpoint is ORR (objective response rate) per mRECIST.

If a subject has progression of disease by mRECIST, it is recommended that the subject be discontinued from the study treatment unless, in the Investigator's opinion, the subject is deriving benefit from treatment.

Clinically stable subjects may continue to receive trial therapy at the discretion of the Investigator. If a repeat scan confirms progression of disease and the subject remains clinically stable, the subject may continue treatment .

Adverse events will be monitored throughout the trial and graded in severity according to the guidelines outlined in the NCI Common Terminology Criteria for Adverse Events (CTCAE) version 4.0.

[figure not shown]
Except as noted above, treatment with pembrolizumab will continue until documented disease progression, unacceptable adverse event(s), intercurrent illness that prevents further administration of treatment, Investigator's decision to withdraw the subject, subject withdraws consent, pregnancy of the subject, noncompliance with trial treatment or procedure requirements, completion of 24 months of pembrolizumab, or administrative reasons requiring the cessation of treatment.

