8.0 METHODOLOGY

8.1 Entry Criteria

8.1.1 Diagnosis/Condition for Entry into the Trial

8.1.2 Subject Inclusion Criteria

In order to be eligible for participation in this trial, the subject must:

1. Be willing and able to provide written informed consent/assent for the trial. The subject may also provide consent for Biomedical Research. However, the subject may participate in the main trial without participating in Biomedical Research.
2. Be ≥ 19 years of age on day of signing informed consent (or acceptable age according to local regulations, whichever is older).
3. Have histologically or cytologically-confirmed diagnosis of gastric or GEJ

adenocarcinoma.

4. Have metastatic disease or locally advanced, unresectable disease.
5. Has experienced documented objective radiographic or clinical disease progression during or after first-line therapy containing any platinum/fluoropyrimidine doublet.
 - a. To be considered as second-line, the subject needs to have the documentation of disease progression on first-line treatment. The disease progression can be confirmed by CT scan or by clinical evidence (such as cytology report from newly developed ascites and plural effusion).
 - b. Any new or worsening malignant effusion (documented by ultrasound) may be confirmed by pathologic criteria (histology and/or cytology) if appropriate.
 - c. A subject experiencing clinical disease progression during or within 6 months following the last dose of adjuvant therapy will be eligible for enrollment provided they received a platinum/fluoropyrimidine doublet as required.
 - d. To be eligible, the subject is required to have received at least one dose of platinum and fluoropyrimidine therapy.
The dose reduction and discontinuation of one of these drugs, switching to/adding new drugs on the first-line treatment is allowed; however, the documentation of disease progression on/after the first-line treatment is required. Therefore, subjects with discontinuation due to adverse events on first-line treatment prior to disease progression are not eligible until disease progression is confirmed by documentation.
6. Have measurable disease based on mRECIST as determined by investigator. Tumor lesions situated in a previously irradiated area are considered measurable if progression has been demonstrated in such lesions.
 - a. Note: The exact same image acquisition and processing parameters should be used throughout the study.

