11.0 STATISTICAL ANALYSIS PLAN

11.1 Statistical Analysis Plan

11.1.1 Efficacy

11.1.1.1 ORR

The intention to treat (ITT) population included all patients who received at least one dose of pembrolizumab. ORR was calculated with two-sided 95% confidence intervals for the overall population. ORR was defined as (CR + PR)/(number of ITT population).

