18.2 Common Terminology Criteria for Adverse Events V4.0 (CTCAE)

The descriptions and grading scales found in the revised NCI Common Terminology Criteria for Adverse Events (CTCAE) version 4.0 will be utilized for adverse event reporting. (<http://ctep.cancer.gov/reporting/ctc.html>)

18.3 Response Evaluation Criteria in Solid Tumors mRECIST Criteria for Evaluating Response in Solid Tumors

Complete response (CR) is the disappearance of any all target lesions;

Partial response (PR) is at least a 30% decrease in the sum of diameters of viable target lesions, taking as reference the baseline sum of the diameters of target lesions;

Progressive disease (PD) is an increase of at least 20% in the sum of the diameters of viable target lesions, taking as reference the smallest sum of the diameters of viable target lesions recorded since the treatment started;

Stable disease (SD) is any cases that do not qualify for either partial response or progressive disease.

Non-target lesions:

CR is disappearance of all non-target lesions

SD is persistence of one or more non-target lesions PD is appearance of one or more new lesions and/or unequivocal progression of existing non-target lesions

mRECIST recommendations:

Pleural effusion and ascites: Cytopathologic confirmation of the neoplastic nature of any effusion that appears or worsens during treatment is required to declare PD.

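### On-study radiotherapy to a target lesion is allowed without a response-counting rule, so radiation shrinkage of a sole or dominant target lesion can count toward the primary ORR

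*Combined protocol and SAP*

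**What the plan says.** Section 8.3.2 lists radiotherapy among the treatments barred during screening and treatment. The Note beneath that item makes an exception: "Radiation therapy to a symptomatic solitary lesion or to the brain may be allowed at the investigator's discretion". The same section then says that subjects who, in the investigator's assessment, "require the use of any of the aforementioned treatments for clinical management should be removed from the trial". Section 8.3 is softer: where a prohibited treatment becomes clinically indicated, "discontinuation from trial therapy or vaccination may be required".

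On the endpoint, section 5.1 states: "The primary efficacy endpoint is ORR (objective response rate) per mRECIST". Section 11.1.1.1 gives the calculation: "ORR was defined as (CR + PR)/(number of ITT population"), with the ITT population being everyone who received a dose. In section 18.3, "Partial response (PR) is at least a 30% decrease in the sum of diameters of viable target lesions", measured against baseline, and for target lesions "Complete response (CR) is the disappearance of any all target lesions". Neither definition mentions local treatment given on study.

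The one rule on irradiated lesions is inclusion criterion 6 in section 8.1.2: "Tumor lesions situated in a previously irradiated area are considered measurable if progression has been demonstrated in such lesions". It decides what may be measured at entry. It does not cover a lesion irradiated after baseline.

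**The concern.** The trial has one arm and is open-label, and its primary endpoint is tumour shrinkage. Radiotherapy to a measured lesion is expected to shrink that lesion whether or not pembrolizumab works. Without a counting rule, such shrinkage enters the numerator of ORR, and no control arm offsets it. The bias runs one way: counting radiation shrinkage can add responses but cannot remove any. Each misattributed response adds 1/40 = 2.5 percentage points. Because few responses are expected under the 5% null, one or two could decide whether the result lies above it.

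**Working it through.** **1. Following the text.** A patient has a symptomatic lesion that was a target at baseline. The investigator uses the Note in 8.3.2 and keeps the patient on study. The lesion is irradiated and shrinks, and later scans are read under 18.3. Nothing there removes the lesion from the sum, and nothing in 11.1.1.1 sets a cut-off at radiotherapy or makes the patient not evaluable. The word *viable* in the PR definition does not help, because tissue made non-viable by radiation also leaves the sum.

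**2. How much shrinkage is needed.** PR is judged on the sum. If the irradiated lesion is a share s of the baseline sum and the other targets do not change, it must shrink by 30%/s:

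| Share of sum | Shrinkage needed for PR |
|---|---|
| 100% (sole target) | 30% |
| 75% | 40% |
| 60% | 50% |
| 50% | 60% |
| 40% | 75% |
| 30% | 100% |

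Below a 30% share, the irradiated lesion cannot produce a PR alone. A new lesion or unequivocal non-target progression is PD under 18.3.

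**3. The plan's own figure.** Section 11.2 gives N = 23 (null 0.05, alternative 0.25, two-sided 0.05, power 0.80), rejecting at 4 or more responses. By exact binomial, P(X ≥ 4 | 23, 0.05) = 2.6% and P(X ≥ 4 | 23, 0.25) = 86.3%. The smallest N meeting 2.5% in the upper tail and 80% power is 21 (rule ≥ 4; 1.9% and 80.8%). The stated 23, from a program that describes its result as approximate, agrees within two patients and is not in dispute.

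**4. A success rule for 40.** The plan enrols 23 + 17 = 40 but gives no critical value for 40. Section 11.1.1.1 plans a two-sided 95% interval without naming the method. I assume the exact (Clopper-Pearson) interval:
- 5/40 = 12.5%, interval 4.2% to 26.8%, includes 5%.
- 6/40 = 15.0%, interval 5.7% to 29.8%, excludes 5%.

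The assumed rule is therefore 6 or more of 40.

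**5. Effect at a true ORR of 5%, given that radiation responses occur.** Each one takes one patient and one response as fixed:
- none: P(X ≥ 6 | 40, 0.05) = 1.4%
- one: P(X ≥ 5 | 39, 0.05) = 4.4%
- two: P(X ≥ 4 | 38, 0.05) = 12.0%

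**6. The same as a rate.** Let q be the share of true non-responders counted as responders through an irradiated lesion. The documents do not give q, so it is assumed. The apparent ORR is 0.05 + 0.95q.
- q = 2.5%: apparent ORR 0.0738, P(X ≥ 6 | 40) = 7.1%
- q = 5%: apparent ORR 0.0975, P(X ≥ 6 | 40) = 19.1%

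**7. Effect at a true ORR of 25%.** The expected count is 40 × 0.25 = 10, and P(X ≥ 6 | 40, 0.25) = 95.7%. One extra response matters only if the true count is 5: P = 98.4% − 95.7% = 2.7%. Two matter only if it is 4 or 5: P = 99.5% − 95.7%, which is 3.9% before rounding.

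**The case against.** The strongest reply is that the exposure is narrow and partly covered by existing text.

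- **Narrow.** Exclusion criterion 9 bars active CNS metastases, so a brain lesion first seen on study is a new lesion and therefore PD. So is any other new symptomatic lesion. What remains is a baseline target lesion that dominates the sum, in a patient with no other progression. Zero such cases in 40 is possible. This stands.
- **Partly covered.** If the removal sentence in 8.3.2 governs, the patient leaves the trial. Flow chart note b and section 10.1.5.4.2 continue imaging only until new anti-cancer treatment starts; 10.1.1.6.3 and 10.1.5.4.3 then move the patient to survival follow-up by telephone. That would end scheduled scans if palliative radiotherapy counts as new anti-cancer treatment, but no section says whether it does. Nor does it reach a patient kept on treatment under the Note. The cover is real on one reading of 8.3.2 and absent on the other.
- **Overcorrection.** Treating every first response after radiotherapy as a non-response could discard a true late response, and section 7.2.3.1 expects some responses to be late. This stands as a cost and is why a lesion-level sensitivity analysis belongs in the fix.

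A reader might also infer three stronger things that the documents do not support. First, that a 30% shrinkage of any irradiated target lesion makes a responder: PR is defined on the sum, so this holds only for a sole target. Second, that the trial's false-positive rate is 4.4% or 12.0%: those figures assume that one or two radiation responses occur. Third, that radiotherapy dates are already collected: section 8.3.1 covers medications and makes dates optional when changes occur, 10.1.1.5.2 covers medication, and 10.1.1.6.2 covers radiation only as prior treatment.

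**Conclusion.** The gap is real and should be closed. Under the stated rules, radiation shrinkage of a target lesion can be credited to pembrolizumab in the primary endpoint when that lesion is the sole target or a large enough share of the sum and nothing else has progressed. The error only raises ORR.

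Its size is conditional on three things: the assumed 6-of-40 rule, an exact interval, and a frequency of radiation responses that the documents do not give. On those terms, one or two such responses matter when the true ORR is near the null and matter little near 25%. The documents do not show that any such case will occur, or that ORR is inflated by a known amount.

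**What to change.** Add to 11.1.1.1, in substance: *Only CR or PR documented before any on-study radiotherapy to a target lesion counts toward ORR. Patients who first meet CR or PR after such radiotherapy are non-responders and stay in the denominator. A sensitivity analysis will treat only the irradiated lesion as not evaluable from the date of radiotherapy.* The sensitivity analysis should state that baseline and later sums are recalculated without that lesion, and that a patient left with no assessable target lesion is a non-responder.

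Confirm that the CRF records the site and date of on-study radiotherapy. Reconcile the Note and the removal sentence in 8.3.2; which of them should govern is a clinical decision outside this point.

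The cost is a short SAP addition and possibly one CRF field. ORR may be slightly less favourable, and a true late response after radiotherapy would not count in the primary analysis. The sensitivity analysis could still credit it if the other target lesions regress.

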8.4 Rescue Medications & Supportive Care

8.4.1 Supportive Care Guidelines

Subjects should receive appropriate supportive care measures as deemed necessary by the treating investigator. Suggested supportive care measures for the management of adverse events with potential immunologic etiology are outlined below and in greater detail in the ECI guidance document. Where appropriate, these guidelines include the use of oral or intravenous treatment with corticosteroids as well as additional anti-inflammatory agents if symptoms do not improve with administration of corticosteroids. Note that several courses of steroid tapering may be necessary as symptoms may worsen when the steroid dose is decreased. For each disorder, attempts should be made to rule out other causes such as metastatic disease or bacterial or viral infection, which might require additional supportive care. The treatment guidelines are intended to be applied when the investigator determines the events to be related to pembrolizumab.

Note: if after the evaluation the event is determined not to be related, the investigator is instructed to follow the ECI reporting guidance but does not need to follow the treatment guidance (as outlined in the ECI guidance document). Refer to Section 5.2.1 for dose modification.

It may be necessary to perform conditional procedures such as bronchoscopy, endoscopy, or skin photography as part of evaluation of the event. Suggested conditional procedures, as appropriate, can be found in the ECI guidance document.

- **Pneumonitis:**

- For **Grade 2 events**, treat with systemic corticosteroids. When symptoms improve to Grade 1 or less, steroid taper should be started and continued over no less than 4 weeks.
- For **Grade 3-4 events**, immediately treat with intravenous steroids. Administer additional anti-inflammatory measures, as needed.
- Add prophylactic antibiotics for opportunistic infections in the case of prolonged steroid administration.

- **Diarrhea/Colitis:**

Subjects should be carefully monitored for signs and symptoms of enterocolitis (such as diarrhea, abdominal pain, blood or mucus in stool, with or without fever) and of bowel perforation (such as peritoneal signs and ileus).

- All subjects who experience diarrhea/colitis should be advised to drink liberal quantities of clear fluids. If sufficient oral fluid intake is not feasible, fluid and electrolytes should be substituted via IV infusion. For Grade 2 or higher diarrhea, consider GI consultation and endoscopy to confirm or rule out colitis.
- For **Grade 2 diarrhea/colitis** that persists greater than 3 days, administer oral corticosteroids.
- For **Grade 3 or 4 diarrhea/colitis** that persists > 1 week, treat with intravenous steroids followed by high dose oral steroids.
- When symptoms improve to Grade 1 or less, steroid taper should be started and continued over no less than 4 weeks.
- **Type 1 diabetes mellitus (if new onset, including diabetic ketoacidosis [DKA]) or \geq Grade 3 Hyperglycemia, if associated with ketosis (ketonuria) or metabolic acidosis (DKA)**
 - For **T1DM or Grade 3-4 Hyperglycemia**
 - Insulin replacement therapy is recommended for Type I diabetes mellitus and for Grade 3-4 hyperglycemia associated with metabolic acidosis or ketonuria.
 - Evaluate patients with serum glucose and a metabolic panel, urine ketones, glycosylated hemoglobin, and C-peptide.
- **Hypophysitis:**
 - For **Grade 2** events, treat with corticosteroids. When symptoms improve to Grade 1 or less, steroid taper should be started and continued over no less than 4 weeks. Replacement of appropriate hormones may be required as the steroid dose is tapered.
 - For **Grade 3-4** events, treat with an initial dose of IV corticosteroids followed by oral corticosteroids. When symptoms improve to Grade 1 or less, steroid taper should be started and continued over no less than 4 weeks. Replacement of appropriate hormones may be required as the steroid dose is tapered.
- **Hyperthyroidism or Hypothyroidism:**

Thyroid disorders can occur at any time during treatment. Monitor patients for changes in thyroid function (at the start of treatment, periodically during treatment, and as indicated based on clinical evaluation) and for clinical signs and symptoms of thyroid disorders.

- **Grade 2** hyperthyroidism events (and **Grade 2-4** hypothyroidism):
 - In hyperthyroidism, non-selective beta-blockers (e.g. propranolol) are suggested as initial therapy.
 - In hypothyroidism, thyroid hormone replacement therapy, with levothyroxine or liothyroinine, is indicated per standard of care.
- **Grade 3-4** hyperthyroidism
 - Treat with an initial dose of IV corticosteroid followed by oral corticosteroids. When symptoms improve to Grade 1 or less, steroid taper should be started and continued over no less than 4 weeks. Replacement of appropriate hormones may be required as the steroid dose is tapered.
- **Hepatic:**
 - For **Grade 2** events, monitor liver function tests more frequently until returned to baseline values (consider weekly).
 - Treat with IV or oral corticosteroids
 - For **Grade 3-4** events, treat with intravenous corticosteroids for 24 to 48 hours.
 - When symptoms improve to Grade 1 or less, a steroid taper should be started and continued over no less than 4 weeks.
- **Renal Failure or Nephritis:**
 - For **Grade 2** events, treat with corticosteroids.
 - For **Grade 3-4** events, treat with systemic corticosteroids.
 - When symptoms improve to Grade 1 or less, steroid taper should be started and continued over no less than 4 weeks.
- **Management of Infusion Reactions:** Signs and symptoms usually develop during or shortly after drug infusion and generally resolve completely within 24 hours of completion of infusion.

Table 4 below shows treatment guidelines for subjects who experience an infusion reaction associated with administration of pembrolizumab (MK-3475).

Table 4 Infusion Reaction Treatment Guidelines

NCI CTCAE Grade	Treatment	Premedication at subsequent dosing
Grade 1 Mild reaction; infusion interruption	Increase monitoring of vital signs as medically indicated until the subject is deemed medically	None

NCI CTCAE Grade	Treatment	Premedication at subsequent dosing
not indicated; intervention not indicated	stable in the opinion of the investigator.	
Grade 2 Requires infusion interruption but responds promptly to symptomatic treatment (e.g., antihistamines, NSAIDS, narcotics, IV fluids); prophylactic medications indicated for <=24 hrs	
Stop Infusion and monitor symptoms. Additional appropriate medical therapy may include but is not limited to:
 
 IV fluids Antihistamines NSAIDS Acetaminophen Narcotics 
Increase monitoring of vital signs as medically indicated until the subject is deemed medically stable in the opinion of the investigator. If symptoms resolve within one hour of stopping drug infusion, the infusion may be restarted at 50% of the original infusion rate (e.g., from 100 mL/hr to 50 mL/hr). Otherwise dosing will be held until symptoms resolve and the subject should be premedicated for the next scheduled dose.
 
Subjects who develop Grade 2 toxicity despite adequate premedication should be permanently discontinued from further trial treatment administration.
	
Subject may be premedicated 1.5h (\pm 30 minutes) prior to infusion of pembrolizumab (MK-3475) with:
 
Diphenhydramine 50 mg po (or equivalent dose of antihistamine).
 
Acetaminophen 500-1000 mg po (or equivalent dose of antipyretic).

Grades 3 or 4 Grade 3: Prolonged (i.e., not rapidly responsive to symptomatic medication and/or brief interruption of infusion); recurrence of symptoms following initial improvement; hospitalization indicated for other clinical sequelae (e.g., renal impairment, pulmonary infiltrates) Grade 4: Life-threatening; pressor or ventilatory support indicated	
Stop Infusion. Additional appropriate medical therapy may include but is not limited to:
 
 IV fluids Antihistamines NSAIDS Acetaminophen Narcotics Oxygen Pressors Corticosteroids Epinephrine 
Increase monitoring of vital signs as medically indicated until the subject is deemed medically stable in the opinion of the investigator. Hospitalization may be indicated.
 
Subject is permanently discontinued from further trial treatment administration.
	No subsequent dosing
Appropriate resuscitation equipment should be available in the room and a physician readily available during the period of drug administration.		

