10.2.4 Evaluating Adverse Events

An investigator who is a qualified physician will evaluate all adverse events according to the NCI Common Terminology for Adverse Events (CTCAE), version 4.0. Any adverse event which changes CTCAE grade over the course of a given episode will have each change of grade recorded on the adverse event case report forms/worksheets.

All adverse events regardless of CTCAE grade must also be evaluated for seriousness.

Table 6 Evaluating Adverse Events

An investigator who is a qualified physician, will evaluate all adverse events as to:

V4.0 CTCAE Grading	Grade 1	Mild; asymptomatic or mild symptoms; clinical or diagnostic observations only; intervention not indicated.
	Grade 2	Moderate; minimal, local or noninvasive intervention indicated; limiting age-appropriate instrumental ADL.
	Grade 3	Severe or medically significant but not immediately life-threatening; hospitalization or prolongation of hospitalization indicated; disabling; limiting self-care ADL.
	Grade 4	Life threatening consequences; urgent intervention indicated.
	Grade 5	Death related to AE
Seriousness	A serious adverse event is any adverse event occurring at any dose or during any use of Merck product that:	
	† Results in death; or	
	† Is life threatening; or places the subject, in the view of the investigator, at immediate risk of death from the event as it occurred (Note: This does not include an adverse event that, had it occurred in a more severe form, might have caused death.); or	
	† Results in a persistent or significant disability/incapacity (substantial disruption of one's ability to conduct normal life functions); or	
	† Results in or prolongs an existing inpatient hospitalization (hospitalization is defined as an inpatient admission, regardless of length of stay, even if the hospitalization is a precautionary measure for continued observation. (Note: Hospitalization [including hospitalization for an elective procedure] for a preexisting condition which has not worsened does not constitute a serious adverse event.); or	
	† Is a congenital anomaly/birth defect (in offspring of subject taking the product regardless of time to diagnosis); or	
	Is a new cancer; (that is not a condition of the study) or	

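### The suggested diarrhea/colitis guidance sets a longer wait before steroids at Grade 3 or 4 (more than 1 week) than at Grade 2 (more than 3 days)

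*Combined protocol and SAP*

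**What the plan says.** The diarrhea/colitis entry in section 8.4.1 has two steroid bullets, one after the other. The first covers the moderate grade (Grade 2) and sets this trigger: "that persists greater than 3 days, administer oral corticosteroids". The second covers both severe grades (3 and 4) together, and its trigger and treatment read: "that persists > 1 week, treat with intravenous steroids followed by high dose oral steroids".

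The opening of 8.4.1 sets the status of this guidance: "Subjects should receive appropriate supportive care measures as deemed necessary by the treating investigator". The measures are described as suggestions that "are outlined below and in greater detail in the ECI guidance document".

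Other entries in the same section treat Grade 3-4 events without a wait. For pneumonitis the instruction is to "immediately treat with intravenous steroids"; for hypophysitis, "treat with an initial dose of IV corticosteroids followed by oral corticosteroids"; for hepatic events, "treat with intravenous corticosteroids for 24 to 48 hours". Table 6 in section 10.2.4 describes Grade 4 as "Life threatening consequences; urgent intervention indicated".

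**The concern.** A steroid trigger would be expected to come no later as the grade rises. Here it comes later. Read literally, a patient at Grade 3 or 4 from onset meets no written steroid trigger on days 4 to 7, while a patient who stays at Grade 2 does. The text offers no interim oral steroid at Grade 3 or 4 to cover those days. It also does not say whether days already spent at Grade 2 count once the event worsens, so a worsening patient could wait longer still.

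What is at stake is patient safety in potentially life-threatening colitis, for which the same section asks the site to watch for bowel perforation. Suggested wording still steers care. The primary analysis is not touched.

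**Working it through.** The plan gives no derived figure to reproduce. The check compares the written durations and then looks for any text that overrides them.

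**Inputs**
- Grade 2 trigger: more than 3 days (8.4.1, diarrhea/colitis).
- Grade 3 or 4 trigger: more than 1 week = 7 days (same entry).
- Convention used here: day 1 is the first day of the event, and a trigger of more than *k* days is met once day *k* has passed.

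**Step 1: difference in the written wait**
- Difference: 7 − 3 = 4 days (days 4 to 7).
- Ratio: 7 / 3 = 2.33.

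**Step 2: a patient who worsens before the Grade 2 trigger is met**

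Let *w* be the number of whole days at Grade 2 before the event becomes Grade 3.
- If Grade 2 days count, the severe trigger passes after day 7. The gap against the Grade 2 trigger is 7 − 3 = 4 days for any *w*.
- If the clock restarts at Grade 3, the trigger passes after day *w* + 7. The gap is (*w* + 7) − 3 = *w* + 4 days.
- Example, *w* = 2 (worsening on day 3): after day 7 or after day 9, so a gap of 4 or 6 days depending on the reading.
- Longest case, *w* = 3 (worsening on day 4, with the Grade 2 trigger just short of being met): under the restart reading, after day 10, a gap of 7 days.

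**Step 3: the other Grade 3-4 steroid entries in 8.4.1**

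| Entry | Steroids at Grade 3-4 | Written wait |
|---|---|---|
| Pneumonitis | IV | None (immediate) |
| Hypophysitis | IV, then oral | None |
| Hyperthyroidism | IV, then oral | None |
| Hepatic | IV for 24 to 48 hours | None |
| Renal failure or nephritis | Systemic | None |
| Diarrhea/colitis | IV, then high-dose oral | More than 7 days |

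Five of the five other organ entries have no wait.

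**Step 4: is there an earlier trigger elsewhere?**
- Table 3 (8.2.1.2) says when to hold or stop pembrolizumab for diarrhea/colitis: hold at Grade 2-3, stop permanently at Grade 4. It mentions corticosteroids only as a dose that must come down to 10 mg or less of prednisone or equivalent per day within 12 weeks, and does not say when they start.
- Section 8.3.2 permits systemic glucocorticoids for suspected immune-related events of clinical interest. It gives no start time.
- The general text of 8.4.1 says steroids are included where appropriate, again without timing.

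The diarrhea/colitis entry is therefore the only place in the protocol that sets a steroid trigger for colitis.

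**The case against.** The strongest reply is that the text does not bind anyone. The measures are suggestions, the investigator decides what is necessary, and section 8.3.2 allows steroids for a suspected immune event from the first day with no condition on grade or duration. The firmer controls do rise with grade and carry no wait: Table 3 holds or stops the drug, and 8.4.1 adds perforation monitoring, fluids and consideration of GI consultation and endoscopy. The ECI guidance document may already give an earlier trigger. All of this stands, and it limits the severity. None of it changes the written trigger. If the ECI document does give an earlier start, the site holds two conflicting instructions.

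A second reply is that diarrhea is handled differently at every grade. It is also the only entry with a steroid wait at Grade 2, plausibly because infection has to be ruled out and colitis confirmed. This weakens the inference that the wait must be zero because the other entries have none. It does not explain why the wait should be longer at Grade 3 or 4, because ruling out other causes applies to every disorder in 8.4.1 and endoscopy is suggested from Grade 2 upward.

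Third, the Grade 4 description in Table 6 is a grading definition, not a treatment instruction, and it says nothing about Grade 3. That is right. It supports the point only for Grade 4 and only as context.

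Fourth, the two triggers lead to different treatments (oral at Grade 2, intravenous then high-dose oral at Grade 3 or 4), so the ratio of 2.3 compares waits for different regimens, and the 4-to-6-day range belongs to one illustrative patient. Both are fair. The firm documentary fact is 7 days against 3.

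**Conclusion.** The concern holds. As written, the steroid trigger for diarrhea/colitis comes 4 days later at Grade 3 or 4 than at Grade 2, and no other text in the protocol corrects it. For a patient who worsens, the gap is 4 days if Grade 2 days count. If they do not, it grows by one day for each day at Grade 2: 6 days in the example above and 7 at most before the Grade 2 trigger would itself have been met.

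This rests on a literal reading of the two bullets and does not assume that investigators would in fact wait. The documents give no rate of Grade 3-4 colitis, so the number of patients affected is unknown; with about 40 subjects it may be small. They also do not state the correct Grade 3-4 interval, so the final value needs medical confirmation. It is a point the sponsor should correct, with high confidence as to the wording and less as to what the site would do in practice.

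**What to change.** Delete the persistence condition from the Grade 3 or 4 diarrhea/colitis bullet in 8.4.1 and leave the rest of the bullet unchanged, so that the intravenous-then-oral regimen applies without a waiting period, as in the other five entries. If a duration is kept for a clinical reason, set it no longer than the 3-day Grade 2 trigger and state that days at Grade 2 count when a patient worsens. The sponsor's medical lead should check the value against the ECI guidance document before the correction is issued, so that the two documents agree.

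The cost is a one-line protocol correction and a memo to the single center. Sample size, the response-rate analysis and data collection do not change.
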